**Table 2: Adverse Events Observed with MGTA-145 and Plerixafor in Phase 1 Study 145-HV-101**

	Part A		Part B		Part C		Part D
	MGTA-145 (0.0075 - 0.3 mg/kg)	Placebo	MGTA-145 + plerixafor (0.015 - 0.15 mg/kg)	Plerixafor	MGTA-145 + plerixafor (0.03 - 0.07 mg/kg)	Plerixafor	MGTA-145 + plerixafor (0.015 - 0.03 mg/kg)
	n=24 n (%)	n=12 n (%)	n=38 n (%)	n=14 n (%)	n=8 n (%)	n=2 n (%)	n=8* n (%)
Subjects with any drug related TEAE	19 (79.2)	-	31 (81.6)	8 (57.1)	6 (75.0)	-	8 (88.9)
Diarrhea	-	-	6 (15.8)	5 (35.7)	1 (12.5)	-	1 (11.1)
Nausea	-	-	7 (18.4)	2 (14.3)	1 (12.5)	-	4 (44.4)
Abdominal discomfort/pain	-	-	5 (13.2)	4 (28.6)	-	-	3 (33.3)
Vomiting	-	-	3 (7.9)	1 (7.1)	-	-	1 (11.1)
Back pain / Musculoskeletal pain 	19 (79.2)	-	24 (63.2)	2 (14.3)	4 (50.0)	-	3 (33.3)
Dizziness / Lightheadedness	-	-	5 (15.6)	1 (7.1)	-	-	4 (44.4)
Headache	-	-	4 (10.5)	1 (7.1)	2 (25.0)	-	2 (22.2)
Dysgeusia	-	-	-	2 (14.3)	-	-	-
Paraesthesia	-	-	2 (5.3)	-	1 (12.5)	-	1 (11.1)

There was no dose response in AEs, so data are aggregated.

 All AEs are grade 1 except for grade 2 abdominal pain (1), nausea (1), and back pain (1) in the plerixafor + MGTA-145 0.075 mg/kg 2h stagger cohort (Part B) and grade 2 headache (1) in the plerixafor + MGTA-145 0.015 mg/kg cohort (Part D).

 Back pain was associated with MGTA-145 infusion, lasted <20 minutes in most cases and did not require medical therapy.

\* A 9th subject enrolled in Part D but did not undergo leukapheresis.

At the 0.03 mg/kg dose, the peak median CD34+ cell count in peripheral blood following MGTA-145 and plerixafor administration was 40 cells/µL (range 18 to 63), which was higher than that observed with plerixafor alone (median 24, range: 13 to 78). The dose of 0.03 mg/kg was determined to be safe and effective, with predictable, dose-linear pharmacokinetics (PK) that are not affected by the coadministration of plerixafor. Administration of plerixafor followed by MGTA-145 after a 2-hour interval was associated with better stem cell mobilization outcomes than administration of plerixafor followed by MGTA-145 after a 10-minute interval, as determined by peripheral blood CD34+ cell counts, and will therefore be the regimen used in this trial.

The median peak CD34+ cell counts observed after administration of various doses of MGTA-145 with plerixafor is provided in [Table 3](#).

Importantly for patients with SCD, for whom substantial apheresis yields of up to 15x10^6 CD34+ cells/kg or more may be required for successful genetic modification and subsequent aHSCT, the 0.03 mg/kg dose of MGTA-145 resulted in the highest median peripheral CD34+ cell count (40 cells/µL (range 18 to 63), as shown in [Table 3](#).

Likewise important for patients with SCD, Phase 1 evaluation demonstrated limited neutrophil activation following MGTA-145 administration, based on changes in L-selectin, CD11b, CD18,

and CD66 from baseline. In the 145-HV-101 study, the 0.03 mg/kg dose of MGTA-145 demonstrated the least change from baseline for these markers of neutrophil activation. Thus, MGTA-145 0.03 mg/kg, in combination with plerixafor 0.24 mg/kg, represents the optimal dosing regimen in patients with SCD, both with regard to subject safety and anticipated mobilization response. Evaluation of the optimal MGTA-145 dose in patients with SCD will provide the greatest opportunity to minimize the number of apheresis sessions required to reliably collect sufficient HSCs, and likely minimize inter-subject variability in mobilization responses, where patients who mobilize poorly may gain incremental benefit from the 0.03 mg/kg dose. Based on similar rationale, investigator-initiated Phase 2 PoC study BMT-362 (conducted under IND 151874) evaluated and has demonstrated that administration of 0.03 mg/kg MGTA-145 in combination with plerixafor safely and successfully mobilizes HSCs for collection in patients with multiple myeloma undergoing aHSCT.

**Table 3: Median peak CD34+ Counts Observed After Administration of Various Doses of MGTA-145 with Plerixafor—Data from Phase I Study 145-HV-101**

Mobilization Regimen	MGTA-145 Dose (mg/kg)	Peak CD34 + Count/ $\mu$ L Median (Range)
MGTA-145 + Plerixafor	0.07	26 (11 to 42)
	0.03	40 (18 to 63)
	0.015	36 (18 to 86)
Placebo + Plerixafor	0	26 (13 to 78)

A regimen of MGTA-145 in combination with plerixafor may provide the potential for greater yield of HSCs, requiring a shorter duration/number of mobilization and apheresis cycles, with improved safety and tolerability in patients with SCD as well as other inherited disorders for which future genetic modification and autologous transplantation may prove curative. Therefore, this Phase 2 PoC study evaluates the efficacy and safety of MGTA-145, administered concomitantly with plerixafor, to patients with SCD for the purpose of HSC mobilization and collection via apheresis.

While patients may benefit from participation in the study (apheresis product will be stored by the investigational sites for potential future transplantation), there is no immediate individual clinical benefit to patients who agree to participate in this study. The study is anticipated to yield important generalizable knowledge about mobilization and apheresis using MGTA-145 in the SCD patient population. The study population is therefore planned to include patients 18 to 35 years of age.

## 5. TRIAL OBJECTIVES AND PURPOSE

The overall objective of Part A is to investigate the efficacy, safety, tolerability, PK, and pharmacodynamics (PD) of a single dose of MGTA-145 for HSC mobilization and apheresis collection when given intravenously (IV) in combination with plerixafor administered SC to patients with SCD.

The overall objective of Part B is to investigate the efficacy, safety, tolerability, PK, and PD of MGTA-145 for HSC mobilization and apheresis collection when given IV in combination with plerixafor administered SC to patients with SCD on 2 consecutive days, using the optimum MGTA-145 dose as determined during Part A.

### 5.1. Part A Objectives and Endpoints

Study objectives and associated endpoints for Part A are listed in [Table 4](#):

**Table 4: Part A Objectives and Endpoints**

Part A Primary Objectives	Part A Primary Endpoints
To characterize the efficacy of a single dose of MGTA-145 and plerixafor for HSC mobilization and apheresis collection in patients with SCD	
 
Determination of the yield of CD34+ cells (CD34+ cells/kg) after 1 dose of MGTA-145 and plerixafor followed by apheresis
 

To characterize the safety and tolerability of MGTA-145 in patients with SCD	
 
Incidence of TEAEs, including drug-related TEAEs, <math>\geq</math>Grade 3 TEAEs, TESAEs, and TEAEs leading to study drug discontinuation
 
Incidence of treatment-emergent <math>\geq</math>Grade 3 clinical laboratory abnormalities
 
Clinically significant changes from baseline in vital signs and laboratory parameters (e.g., serum chemistry, hematology)
 

To measure the mobilization effects of single-day dosing with MGTA-145 and plerixafor in the peripheral blood in patients with SCD	
 
Determination of peak peripheral blood CD34+ counts
 

To characterize the PK profile of MGTA-145 in patients with SCD	
 
Determination of PK exposures
 

To characterize the immunogenicity of MGTA-145 in patients with SCD	
 
Presence and titers of anti-drug antibodies
 

Part A Exploratory Objectives	Part A Exploratory Endpoints
To characterize the phenotype and function of cells collected by apheresis in patients with SCD	
 
Flow cytometric characterization of cells collected following MGTA-145 and plerixafor mobilization and apheresis
 
Characterization of hematopoietic cell function by mouse engraftment studies and/or colony formation assays
 

To assess gene-modifying potential of mobilized CD34 + cells in patients with SCD	
 
Assessment of ability to select and gene-modify CD34+ cells
 

HSC=hematopoietic stem cells; PD=pharmacodynamic(s); PK=pharmacokinetic(s); SCD=sickle cell disease; TEAE=treatment-emergent adverse event; TESAE=treatment-emergent serious adverse event	

## 5.2. Part B Objectives and Endpoints

Study objectives and associated endpoints for Part B are listed in [Table 5](#):

**Table 5: Part B Objectives and Endpoints**

Part B Primary Objectives	Part B Primary Endpoints
To characterize the efficacy of 2 consecutive days of dosing with MGTA-145 and plerixafor for HSC mobilization and apheresis collection in patients with SCD	
 
Determination of the yield of CD34+ cells after 2 consecutive days of MGTA-145 and plerixafor mobilization and apheresis collection in patients with SCD
 

To characterize the safety and tolerability of	
 
Incidence of TEAEs, including drug-related TEAEs, <math>\geq</math>Grade 3 TEAEs, TESAEs, and TEAEs leading to study drug discontinuation
 

MGTA-145 in patients with SCD	
 
Incidence of treatment-emergent <math>\geq</math>Grade 3 clinical laboratory abnormalities
 
Clinically significant changes from baseline in vital signs and laboratory parameters (e.g., serum chemistry, hematology)
 

Part B Secondary Objectives	Part B Secondary Endpoints
To measure the mobilization effects of 2 consecutive days of dosing with MGTA-145 and plerixafor in the peripheral blood in patients with SCD	
 
Determination of peak peripheral blood CD34<math>^{+}</math> counts
 

To characterize the PK profile of MGTA-145 in patients with SCD	
 
Determination of PK exposures
 

To characterize the immunogenicity of MGTA-145 in patients with SCD	
 
Presence and titers of anti-drug antibodies
 

Part B Exploratory Objectives	Part B Exploratory Endpoints
To characterize the phenotype and function of cells collected by apheresis in patients with SCD	
 
Flow cytometric characterization of the cells collected following MGTA-145 and plerixafor mobilization and apheresis
 
Characterization of hematopoietic cell function by mouse engraftment studies and/or colony formation assays
 

To assess gene-modifying potential of mobilized HSC in patients with SCD	
 
Assessment of the ability to select and gene-modify CD34<math>^{+}</math> cells
 

HSC=hematopoietic stem cell; PD=pharmacodynamic(s); PK=pharmacokinetic(s); TEAE=treatment emergent adverse event; TESAE=treatment-emergent serious adverse event
	

## 6. INVESTIGATIONAL PLAN

[figure not shown]
### 6.1. Overall Study Design

This Phase 2, multicenter, open-label study will be conducted in 2 parts (Parts A and B). Part A is intended to characterize the efficacy, safety, PK, and PD of a single dose of MGTA-145 and plerixafor for HSC mobilization and apheresis collection in patients with SCD. Part B is intended to characterize the efficacy of 2 consecutive days of dosing with MGTA-145 and plerixafor for HSC mobilization and apheresis collection in patients with SCD.

The study design and subject procedural flow schematic for Parts A and B are illustrated in [Figure 1](#). The Schedule of Assessments for Part A is provided in

[Table 6](#), and the Schedule of Assessments for Part B is provided in [Table 7](#). The Schedule of Assessments for blood and immune cell composition for Parts A and B is provided in [Table 8](#).

**Figure 1: Part A (Single Dose) and Part B (Single Dose on 2 Consecutive Days)**

**Table 6: Schedule of Assessments: Part A (Single Dose)**

Study Period Procedures	Screening	Baseline	Mobilization /Apheresis	1-week follow-up (Day 7 to 10) b	End of Study (Day 30) b
	Day -30 to -2	Day -1	Day 1		
Informed consent	X				
Medical history	X	X			
Inclusion/exclusion criteria review	X				
Height		X			
Weight		X		X	
Physical examination	X	X		X	
Symptom-directed physical examination			X		
Vital signs a	X	X	X	X	
Serology c	X				
Serum or urine $\beta$ -hCG (females)	X	X			
12-lead ECG	X				
Urinalysis		X	X	X	
Chemistry d	X	X	X	X	
Hematology e	X	X	X	X	
Anti-drug antibodies		X		X	
Plerixafor administration			X		
MGTA-145 administration f			X		
Apheresis procedure			X		
Apheresis yield g			X		
PROMIS and ASCQ-Me questionnaires h			X	X	
Non-serious AEs and SAEs i	X	X	X	X	X j
Concomitant medications	X	X	X	X	X j

AE=adverse event; ASCQ-Me=Adult Sickle Cell Quality of Life Measurement Information; BPI=Brief Pain Inventory;  $\beta$ -hCG=beta-human chorionic gonadotropin; CFU= colony-forming unit; ECG=electrocardiogram; PK=pharmacokinetics; NRS=Numeric Rating Scale; SAE=serious adverse event

a Vital sign measurements will be taken in the sitting position after the subject has been resting for 5 minutes. Vital signs should be taken before any blood samples are drawn.

b If a subject does not complete dosing, there will not be follow-up visits. If a subject received MGTA-145 but did not complete apheresis, then follow-up visits are required.

c All subjects enrolled in Parts A will be screened for human immunodeficiency virus (HIV), hepatitis B surface antigen (HBsAg), human T-cell leukemia virus (HTLV), and hepatitis C virus (HCV) at the screening visit. Subjects who are HCV antibody positive must have a HCV ribonucleic acid (RNA) polymerase chain reaction (PCR) test.

d Clinical chemistry consists of sodium, potassium, chloride, bicarbonate, blood urea nitrogen, creatinine, glucose, calcium, aspartate aminotransferase (AST), alanine aminotransferase (ALT), alkaline phosphatase, albumin, total and indirect bilirubin. Clinical chemistry sample collection should be done prior to dosing on Day 1. All other clinical chemistry sample collections will be done on the morning of the assessment day.

e Hematology is complete blood count (CBC) with platelets and leukocyte differential. Hematology sample collection should be done prior to dosing on Day 1 and Day 2. All other hematology sample collections will be done on the morning of the assessment day.

f MGTA-145 is to be administered via a 3 to 10-minute IV infusion, approximately 2 hours after plerixafor SC injection. Instructions regarding administration are provided in the Study Pharmacy Manual.

g Total nucleated cell count and CD34+ cell count in absolute numbers and per kg.

h ASCQ-Me® and PROMIS® questionnaires will be completed prior to dosing on Day 1.

i Collection of non-serious AEs and SAEs will begin once the Informed Consent Form (ICF) has been signed. Any SAE occurring after the reporting period must be promptly reported if a causal relationship to study drugs is suspected.

j End-of-study visit phone call will occur 30 days ( $\pm 3$  days) after the last dose of MGTA-145 was received, to assess adverse events and concomitant medications.

**Table 7: Schedule of Assessments: Part B (Single Dose on 2 Consecutive Days)**

Study Period Procedures	Screening	Baseline	Mobilization/Apheresis b		1-week follow-up (Day 8 to 11) c	End of Study (Day 30) c
	Day -30 to -2	Day -1	Day 1 Part B	Day 2 Part B only		
Informed consent	X					
Medical history	X	X				
Inclusion/exclusion criteria review	X					
Height		X				
Weight		X			X	
Physical examination	X	X			X	
Symptom-directed physical examination			X	X		
Vital signs a	X	X	X	X	X	
Serology d	X					
Serum or urine $\beta$ -hCG (females)	X	X				
12-lead ECG	X					
Urinalysis		X	X	X	X	
Chemistry e	X	X	X	X	X	
Hematology f	X	X	X	X	X	
Anti-drug antibodies		X			X	
Plerixafor administration			X	X		
MGTA-145 administration g			X	X		
Apheresis procedure			X	X		
Apheresis yield h			X	X		
PROMIS and ASCQ-questionnaires i			X		X	
Non-serious AEs and SAEs j	X	X	X	X	X	X k
Concomitant medications	X	X	X	X	X	X k

AE=adverse event; ASCQ-Me=Adult Sickle Cell Quality of Life Measurement Information; BPI=Brief Pain Inventory;  $\beta$ -hCG=beta-human chorionic gonadotropin; CFU= colony-forming unit; ECG=electrocardiogram; PK=pharmacokinetics; NRS=Numeric Rating Scale; SAE=serious adverse event

a Vital sign measurements will be taken in the sitting position after the subject has been resting for 5 minutes. Vital signs should be taken before any blood samples are drawn.

b For Part B, mobilization/collection will occur on 2 consecutive days.

c If a subject does not complete dosing, there will not be follow-up visits. If a subject received MGTA-145 but did not complete apheresis, then follow-up visits are required.

d All subjects enrolled in Part B will be screened for human immunodeficiency virus (HIV), hepatitis B surface antigen (HBsAg), human T-cell leukemia virus (HTLV), and hepatitis C virus (HCV) at the screening visit. Subjects who are HCV antibody positive must have a HCV ribonucleic acid (RNA) polymerase chain reaction (PCR) test.

e Clinical chemistry consists of sodium, potassium, chloride, bicarbonate, blood urea nitrogen, creatinine, glucose, calcium, aspartate aminotransferase (AST), alanine aminotransferase (ALT), alkaline phosphatase, albumin, total and indirect bilirubin. Clinical chemistry sample collection should be done prior to dosing on Day 1 and Day2. All other clinical chemistry sample collections will be done on the morning of the assessment day.

f Hematology is complete blood count (CBC) with platelets and leukocyte differential. Hematology assessments will be done on the morning of the assessment day.

g MGTA-145 is to be administered via a 3 to 10-minute IV infusion, approximately 2 hours after plerixafor SC injection. Instructions regarding administration are provided in the Study Pharmacy Manual.

h Total nucleated cell count and CD34+ cell count in absolute numbers and per kg.

i ASCQ-Me® and PROMIS® questionnaires will be completed prior to dosing on Day 1.

j Collection of non-serious AEs and SAEs will begin once the Informed Consent Form (ICF) has been signed. Any SAE occurring after the reporting period must be promptly reported if a causal relationship to study drugs is suspected.

k End-of-study visit phone call will occur 30 days ( $\pm$ 3 days) after the last dose of MGTA-145 was received, to assess adverse events and concomitant medications.

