After the second cohort has completed the 1-week follow-up visit, the DMC will likewise evaluate the safety, PK, and mobilization kinetics of MGTA-145 before subjects may be enrolled into Part B. Criteria for the DMC recommendations regarding cohort progression and dosing regimen will be defined in the DMC Charter.

**Part B:** Part B has a planned enrollment of approximately 3 evaluable subjects. Subjects will receive single doses of MGTA-145 and plerixafor on 2 consecutive days, followed by apheresis on each dosing day. The dose of MGTA-145 will be identical to that of the second Part A cohort, unless otherwise recommended by the DMC.

All subjects in Parts A and B will be observed at the investigational site from Day -1 until at least one day after the last apheresis, attend a 1-week follow-up visit 7 to 10 days after the last MGTA-145 infusion, and attend an end-of-study phone visit approximately 30 days after the last MGTA-145 infusion.

Hematopoietic stem cells obtained by apheresis (HPC-A) will be processed according to standardized clinical cell therapy laboratory procedures. Peripheral blood and HPC-A will be stored for testing (e.g., exploratory pharmacodynamic (PD) evaluation, cell characterization, and process characterization) and approximately  $2 \times 10^6$  CD34+ cells/kg are to be cryopreserved at clinical sites for potential future use by study subjects as backup reserve, should subjects decide to proceed with allogeneic hematopoietic cell transplant or autologous gene therapy.

**Overall Objectives:** The overall objective of Part A is to investigate the efficacy, safety, tolerability, PK, and PD of a single dose of MGTA-145 for HSC mobilization and apheresis collection when given IV, in combination with plerixafor administered SC, to patients with SCD.

The overall objective of Part B is to investigate the efficacy, safety, tolerability, PK, and PD of MGTA-145 for HSC mobilization and apheresis collection when administered IV, in combination with plerixafor administered SC, to patients with SCD on 2 consecutive days, using the optimum MGTA-145 dose as determined during Part A.

**Objectives and Endpoints:** Study objectives and associated endpoints for Part A are listed below:

Part A Primary Objectives	Part A Primary Endpoints

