All subjects in Parts A and B will be observed at the investigational site from Day -1 until at least one day after the last apheresis and attend a 1-week (7 to 10 days) follow-up visit after the last MGTA-145 infusion. All subjects will attend an EOS phone visit 30 days after the last MGTA-145 infusion.

For both Parts A and B, peripheral CD34+ cell counts will be performed pre- and post-dosing with plerixafor and post-dosing with MGTA-145, up to 5 minutes prior to apheresis ([Table 8](#)).

Hematopoietic stem cells obtained by apheresis (HPC-A) will be processed according to standardized clinical cell therapy laboratory procedures. Peripheral blood and HPC-A will be stored for testing (e.g., exploratory PD evaluation, cell characterization, and process characterization) and by the investigational sites for potential future transplantation.

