### 6.6.1.3. Unscheduled Stopping Rule Assessment

In addition to the cohort stopping rules outlined above, if within approximately one week (up until the 1-week follow-up visit) after MGTA-145 dosing, any subject develops a Grade  $\geq 4$  VOE, or a Grade  $\geq 3$  drug-related TEAE (based on the National Cancer Institute (NCI) Common Terminology Criteria for Adverse Events (CTCAE) version 5.0) other than VOE, dosing of the current cohort will not be continued until the DMC assesses whether dosing may continue and whether dosing modifications are needed. In addition to VOEs, Grade 3 AEs known to be associated with plerixafor (i.e., nausea, vomiting, diarrhea, headache [as per plerixafor label]) or MGTA-145 (i.e., musculoskeletal pain that is less than 1 hour in duration from the time pain is first reported) will not count toward this stopping rule.

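### The schedule footnotes cancel follow-up visits when dosing is incomplete, which for a Part B subject given only the first MGTA-145 infusion conflicts with the visits the protocol requires of all subjects

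*Protocol*

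**What the plan says.** Table 7 footnote c (Part B) and Table 6 footnote b (Part A) carry the same two sentences. The first reads: "If a subject does not complete dosing, there will not be follow-up visits". The second reads: "If a subject received MGTA-145 but did not complete apheresis, then follow-up visits are required".

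The rest of the protocol describes follow-up without that exception:

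- The Synopsis (Methodology) has all subjects in both parts "attend a 1-week follow-up visit 7 to 10 days after the last MGTA-145 infusion".
- Section 6.3 repeats this and adds: "All subjects will attend an EOS phone visit 30 days after the last MGTA-145 infusion".
- Section 11.2.1 collects serious and non-serious adverse events from consent to the end-of-study visit.
- Section 12.1 puts every enrolled subject who received a dose of MGTA-145 in the safety set.
- Section 7.3 does not treat a subject who stops study procedures as withdrawn unless consent is withdrawn.

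Section 11 foresees incomplete dosing in Part B: if a VOE follows the first infusion, the investigator decides whether the second is given.

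**The concern.** Whether the 1-week visit and the end-of-study call take place is settled during the trial. A visit that was not held cannot be recovered by any analysis rule written later. If a site follows the first footnote sentence literally for a Part B subject who had one infusion, that subject is counted in the safety denominators but contributes no scheduled data after the on-site stay.

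In Part B the incidence of treatment-emergent adverse events, Grade 3 or higher laboratory abnormalities and changes in laboratory values and vital signs are primary endpoints, and anti-drug antibodies are a secondary endpoint. The 1-week visit supplies data for all of them. By the route that Section 11 describes, the subject affected would be one who has just had a VOE, so the missing data would not be a random subset.

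**Working it through.** The protocol gives no figure on this point. The check is a comparison of the texts case by case, followed by a count of what is scheduled after the first infusion.

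**Step 1: the cases.** *Silent* means that the sentence does not address the case.

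| Case | Footnote, first sentence | Footnote, second sentence | Synopsis and Section 6.3 |
|---|---|---|---|
| Part B, first infusion only | no visits | visits, if completing apheresis means both sessions; silent if the Day 1 session is enough | visits |
| Infusion interrupted, apheresis not completed | no visits | visits | visits |
| Infusion interrupted, apheresis completed | no visits | silent | visits |
| Plerixafor only | no visits | silent | no infusion date to count from |
| Full dosing, apheresis not completed | silent | visits | visits |

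The first row is the one the protocol itself foresees. The next two need an interrupted infusion of 3 to 10 minutes, which is remote, and they are the only way the conflict arises in Part A. The fourth row is a weaker conflict, because the visits are timed from an infusion that did not happen. The fifth shows none.

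**Step 2: are the two terms defined elsewhere?**

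- *Complete dosing*: the nearest text is Section 8.3, which defines compliance as receiving 100% of the planned dosage. The footnotes do not refer to it. If it applied, a one-infusion Part B subject would fall under the cancellation.
- *Complete apheresis*: Section 10.2.2 gives only a maximum of 8 hours. Section 12.1 counts the two Part B sessions separately and speaks of successful completion without a criterion. Table 7 footnote b says "For Part B, mobilization/collection will occur on 2 consecutive days", which suggests both sessions but does not say so.

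**Step 3: scheduled data after the first infusion, from Tables 6 and 7.**

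| Item | Full schedule | Literal first sentence |
|---|---|---|
| Anti-drug antibody samples (either part) | 1 (1-week visit; the other sample is at baseline) | 0 |
| Chemistry and hematology, Part B one-infusion subject | 2 (Day 2 morning and 1-week visit) | 2 − 1 = 1, if the Day 2 sample is still drawn |
| Chemistry and hematology, Part A | 1 (1-week visit) | 0 |
| Scheduled adverse-event contacts after the on-site stay | 2 (1-week visit, end-of-study call) | 0 |

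The Part A laboratory count rests on the Day 1 samples preceding dosing. Table 6 footnote d says "Clinical chemistry sample collection should be done prior to dosing on Day 1" and footnote e says "Hematology sample collection should be done prior to dosing on Day 1 and Day 2". Table 6 has no Day 2 column, so only the 1-week sample follows dosing.

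**The case against.** The strongest reply is that the two footnote sentences are meant as a pair: the first covers subjects who never received MGTA-145, the second those who did. That reading fits a follow-up schedule timed from the last MGTA-145 infusion and a safety set that requires a dose of it. It largely resolves Part A. In Part B, Table 7 footnote b plans collection on two days, so a subject stopped after Day 1 has arguably not completed apheresis, and the second sentence would then require the visits. A site might well hold them.

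This limits the point but does not remove it. The first sentence is not confined to subjects without MGTA-145, and the second is not written as an exception to it. For a subject who finished the Day 1 session, whether the second sentence applies turns on an undefined term, and the nearest definition bearing on dosing (Section 8.3) points towards cancellation.

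A reader might go further in three ways that the protocol does not support.

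- *The unscheduled stopping rule loses its end point.* Section 6.6.1.3 opens "if within approximately one week (up until the 1-week follow-up visit) after MGTA-145 dosing, any subject develops a Grade" and then names the qualifying grades. The window is bounded by time, since Section 6.6.1 gives 7 to 10 days. A Grade 4 or higher VOE would ordinarily meet the seriousness criteria of Section 11.2.4, and serious events are reported within 24 hours under Section 11.5. The scheduled VOE rules and their probabilities concern Part A.
- *The frequency can be read off the VOE rates.* At the 30% rate, the chance that at least 1 of 3 subjects has a VOE is 1 − 0.7³ = 65.7%. But that rate is for Grade 3 or higher events during and after apheresis, not for the interval between two consecutive-day infusions, and a VOE leads only to a discretionary decision.
- *Section 11.4 cancels follow-up too.* It narrows what is recorded after premature discontinuation and can be read as a specific exception. It cancels no visit and is a separate matter.

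**Conclusion.** The conflict is real and worth correcting, and its reach is narrow. It matters for a Part B subject who receives the first MGTA-145 infusion but not the second. On the literal reading of the first footnote sentence, that subject remains in the safety set and loses 1 of 1 scheduled post-dose antibody samples, the 1-week laboratory tests and 2 of 2 remaining scheduled adverse-event contacts. The conflict with the Synopsis and Sections 6.3 and 11.2.1 does not depend on how apheresis is defined; the conflict with the footnote's second sentence does.

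The loss has limits. The event that stopped dosing is already recorded, Section 11.2.2 follows treatment-related and all serious events to resolution or stabilization, and Section 11.5 keeps serious events reportable through end of study. What has no substitute is the antibody sample, the 1-week laboratory values and scheduled questioning about later non-serious events.

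Two figures might be taken as the size of the effect and should not be. Counting 30 − 1 = 29 of 30 days without scheduled contact ignores that the full schedule already leaves 30 − 10 = 20 to 30 − 7 = 23 days between the 1-week visit and the call. A one-infusion subject is not evaluable under Section 12.1, so with the 3 evaluable subjects required by Section 12.5 he or she would be 1/(3 + 1) = 25% of the Part B safety set. That is a share of a very small group if the case occurs, not an expected loss. How often it would occur cannot be derived from the protocol.

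**What to change.** Reconcile Table 7 footnote c and Table 6 footnote b with the Synopsis and Sections 6.3, 11.2.1 and 12.1. State what *complete dosing* and *complete apheresis* mean in Part B, in particular whether completing apheresis refers to one session or both. The result should be that the footnotes do not cancel the 1-week and end-of-study data collection that the text on all subjects already requires for anyone in the safety set. How the passages are brought into line, including for a subject who received plerixafor only, is for the sponsor to decide.

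The cost is the wording of two footnotes and two definitions and, in conduct, at most one visit and one call for very few subjects. It needs to be settled before Part B enrolment, because visits not held cannot be made up later.
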